Allogeneic HB-adMSCs to provide immune support against COVID-19.

- The patient develops a severe allergic reaction that occurs following investigational product administration.

A patient may voluntarily withdraw or be withdrawn from the study at any time for reasons including, but not limited to, the following:

- Patient withdrawal of consent: At any time, a patient's participation in the study may terminate at his/her request. The specific reason for patient withdrawal will be noted on the case report form (CRF).
- Lost to follow-up: The patient stops coming for visits, and study personnel is unable to contact the patient after repeated attempts (e.g., mail, or email).
- This study may be terminated at the discretion of the Sponsor or any regulatory agency.

If a patient's infusions are discontinued at any point during the trial and the patient maintains consent to contribute additional outcome information, the patient should continue to be followed through Week 26 for all safety and efficacy assessments. Investigators will be trained about the importance of retention and steps to prevent missing data.

The date and reason for withdrawal are to be documented in the CRF. The study site must immediately notify the medical monitor. The patients who withdraw prematurely must attend an early discontinuation visit if possible, at which time they will complete all assessments described in Table 2 under the Week 24 visit.

In the event that a patient discontinues prematurely from the study due to an Adverse Event (AE) or serious AE, the event will be followed until it resolves (returns to normal or baseline values) or stabilizes, or until it is judged by the Investigator to be no longer clinically significant. Once a patient is withdrawn from the study, the patient may not re-enter the study. If the subject develops symptoms associated with COVID-19 during the conduct of this study, they will be asked to consult their personal physician and be tested for COVID-19, and to self-quarantine for at least 14 days. Quarantine must occur while waiting for COVID-19 test results. Once asymptomatic, subject may resume site visits. If the test results are positive, the subject will be asked to quarantine and may continue to receive infusions at the quarantine site. If the subject develops severe symptoms (i.e., shortness of breath/difficulty breathing) they should go to the ER instead of personal physician.

Treatments

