It is the responsibility of the Principal Investigator to oversee the safety of the study at his/her site. This safety monitoring will include careful assessment and appropriate reporting of adverse events as noted above. At Hope Biosciences, [name], MD [contact] will be responsible for reviewing any reported AEs and SAEs to determine if changes to the study need to be made or if the study should be stopped for the protection of patients. DSMB will review all deaths (to assure non-attribution), cases of anaphylaxis or suspected anaphylaxis, thromboembolic events, new malignancy/tumor, infections/hospitalizations (including unrelated to COVID-19 but due to underlying condition). After 15 subjects diagnosed with COVID-19, 5 subjects are hospitalized, or 3 subjects in the ICU, DSMB will review. DSMB will also review safety data at mid-point of the study.

Risks

Potential Risks of the Investigational Product and Clinical Investigation

Risks Associated with HB-adMSCs

Respiratory Risks:

A potential risk is that the infusion could initiate a VTE event with subsequent cardiopulmonary sequelae of respiratory failure and/or right heart strain/failure. We plan to monitor oxygen saturation, and respiratory rate/work of breathing for the first 2 hours post- infusion. The patient will be examined for VTE events (clinical exam, oxygen saturation) during each infusion visit and at each follow-up visit.

Hepatic Risks:

The reticuloendothelial system can sequester immature blood elements, theoretically resulting in hepatic injury. An acute elevation of the AST/ALT hepatic enzymes > 900 U/dl post-infusions will be considered an infusion related adverse event. This level is based upon the organ system scoring definitions for moderate hepatic failure and corresponds to the CTCAE v4.03 Grade 4 adverse event. It is unlikely that "end vessel" micro-thrombosis would occur in the liver due to the dual blood supply of the liver and the lung is the first pass organ. A CMP will be obtained at follow-up visits.

Coagulation Cascade:

A coagulation panel will be obtained at screening, baseline, infusion and the follow-up visits. The patient will be monitored for the development of venous thromboembolic events (see pulmonary monitoring above) as well as for the development of clinical deep vein thrombosis (limb swelling, tenderness, discoloration).

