Subjects may benefit from their participation in the study by experiencing an overall feeling of well-being. Subjects enrolled in the study will be contributing to the advancement of science and to future investigations regarding stem cells and possible therapeutic applications, including treatment and prevention of respiratory diseases, specifically COVID-19.

Statistical Analysis

Determination of Sample Size

Sample size calculation was determined based upon the number of patients currently banked at our facility and those who are already registered to bank. Sample size for this study is not to exceed 53 patients.

Null hypothesis- Efficacy

Treatment with HB-adMSCs does not cause changes in primary and secondary endpoints (listed below) for providing immune support against Coronavirus Disease.

Alternative hypothesis-Efficacy

The alternative hypothesis for this study is that HB-adMSCs treatment does result in changes from baseline values of primary and secondary endpoints in patients.

Null hypothesis-Safety

Treatment with HB-adMSCs results in adverse or serious adverse events and/or detrimental changes in laboratory values, vital signs, weight, X-rays, ECG, or physical examination determined to be related to the study drug.

Alternative hypothesis-Safety

HB-adMSCs treatment for COVID-19 does not result in adverse or serious adverse events and/or detrimental changes in laboratory values, vital signs, weight, X-rays, ECG, or physical examination determined to be related to the study drug.

Endpoints

The endpoints measured in this study are safety and clinical efficacy.

Safety is assessed by incidence of adverse and serious adverse events, incidence of specific adverse events including serious infections, infusion-related reactions, hepatotoxicity, heart failure, and cytopenia. Clinically significant changes in laboratory values, vital signs, weight, and physical examination results will also be measured.

Allogeneic HB-adMSCs to provide immune support against COVID-19.

Clinical efficacy is assessed by primary and secondary endpoints. Primary endpoints include incidence of hospitalization for COVID-19, incidence of symptoms associated with COVID-19, and severity of symptoms associated with COVID-19. Secondary endpoints include absence of upper/lower respiratory tract infections, change from baseline in inflammation, SF-36 and PHQ9 questionnaires.

Analysis Population

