8.1. Adverse Events Analyses

Adverse events (AES) are summarised descriptively. AE data will be displayed in terms of the number of subjects with at least one event (N), percentage of subjects with at least one event (%), the number of events (E) and the event rate per 100 years of exposure (R).

Summaries of AEs and of serious AEs will be presented as an overview including all AEs, serious AEs, AEs by severity, AEs by relation to treatment, action to AEs and treatment advised, and outcome of AEs.

Furthermore, summary tables based on reported terms are made for:

- All AEs
- Serious AEs
- AEs leading to withdrawal of study

Individual adverse events will be listed.

The details of the planned displays are in Appendix 5: List of Data Displays.

Protocol Number: HBCOVID02
Hope Biosciences
Statistical Analysis Plan

Confidential

Date: 14-Oct-2021
Version: 1.0
Status: Final

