8.2. Clinical Laboratory Analyses

Laboratory evaluations including the analyses of Biochemistry laboratory tests, Hematology laboratory tests and Coagulation tests (PTT/PT/INR). The details of the planned displays are in Appendix 5: List of Data Displays.

All laboratory parameters, including numerical urine analysis parameters will be summarised descriptively. Also, p-value for treatment difference using Analysis of variance (ANOVA) is displayed for lab parameters. Categorical urine analysis results will be summarized using count and percentage based on subjects.

Change from baseline will be summarised descriptively. Also, p-value for treatment difference using one-way Analysis of variance (ANOVA) is displayed for change from baseline.

Individual laboratory evaluations will be listed.

Data recorded at unscheduled assessments will not be included in tables and figures but will be listed.

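### The supplied SAP tabulates adverse events by reported term and plans no incidence by arm for the five adverse event groups that the protocol uses to assess safety

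*SAP*

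**What the plan says.** In the protocol, the Endpoints paragraph under Statistical Analysis says safety is assessed by the incidence of AEs and SAEs and by the "incidence of specific adverse events including serious infections, infusion-related reactions, hepatotoxicity, heart failure, and cytopenia". Under Hepatic Risks the protocol gives one numerical criterion that bears on these groups: "An acute elevation of the AST/ALT hepatic enzymes > 900 U/dl post-infusions will be considered an infusion related adverse event".

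SAP 8.1 plans two kinds of AE summary. The first is an overview of all AEs and serious AEs, with "AEs by severity, AEs by relation to treatment, action to AEs and treatment advised, and outcome of AEs". The second is by term: "summary tables based on reported terms are made for" all AEs, serious AEs and "AEs leading to withdrawal of study". Individual events are listed. For the rest, "The details of the planned displays are in Appendix 5: List of Data Displays"; that appendix is not in the supplied text, which ends at section 9.

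For laboratory data, SAP 8.2 says "Change from baseline will be summarised descriptively", with ANOVA p-values. SAP 8.3 treats physical examination and vital signs with counts, descriptive statistics and ANOVA.

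**The concern.** The protocol names five clinical groups whose incidence is to measure safety. The SAP's by-term tables follow whatever wording was reported, and neither document mentions a dictionary, preferred terms, organ classes or term groupings. One kind of event written in several ways can therefore occupy several rows, and no planned summary adds those rows up by subject.

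This matters because the trial compares three doses with placebo in very small arms, and the protocol itself says the product's risks in this population are unknown. A dose-related pattern in infusion reactions, for example, can be seen only if subjects with such a reaction are counted together, by arm. If groupings are chosen after the data are unblinded, the choice of terms can shape the result.

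A smaller matter concerns the third by-term table, which covers withdrawal from the study. The protocol asks that when infusions are discontinued and the patient keeps consent, "the patient should continue to be followed through Week 26 for all safety and efficacy assessments". Such a patient has not withdrawn from the study and so does not enter that table.

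**Working it through.** There is no planned figure to reproduce, so the first step is to set the protocol's five groups against the supplied SAP text.

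| Group in the protocol | Nearest supplied SAP analysis | What it yields |
|---|---|---|
| Serious infections | Serious AE table and overview (8.1) | Rows by reported term; a count of subjects with any serious AE. The list in 7.2.1 omits the respiratory-infection endpoint, so no cover comes from there |
| Infusion-related reactions | By-term tables and relation to treatment (8.1); vital signs (8.3) | Rows by term; subjects with any related AE; vital-sign summaries |
| Hepatotoxicity | Biochemistry (8.2) | Descriptive values and ANOVA; no case count, and the protocol's AST/ALT criterion is not carried over |
| Heart failure | By-term tables (8.1) | Rows by reported term |
| Cytopenia | Haematology (8.2) | Descriptive values and ANOVA; no case count |

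SAP 8.2 also keeps results from unscheduled assessments out of tables and figures. The protocol's Unscheduled Visits section intends those visits especially for AEs that need follow-up, so an abnormal value found there reaches only a listing.

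The second step is the size of the effect.

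**Arm size.** Both documents give 53 subjects, allocated 3:1 to active and placebo. Active: 53 × 3/4 = 39.75, about 40. Each arm: 53/4 = 13.25, about 13, assuming the three doses are equal in size. (The protocol synopsis also gives 25 per group. That would be 100 subjects and does not fit 53, so I use 53.)

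**Assumptions, not in the documents.** A reaction has true incidence p of 15% or 30% in an arm. Each affected subject is recorded under one term, and the terms are split evenly over k rows. k = 1 is the grouped row that the fix would give.

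**Formulas.** With q = p/k:

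- expected subjects per row = 13q
- chance that a given row shows 3 or more = 1 − Σ C(13, j) q^j (1 − q)^(13 − j), summed over j = 0, 1, 2

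Three subjects is only a marker for a row that a reader would notice.

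Worked case, p = 15%, k = 3, q = 0.05: expected 13 × 0.05 = 0.65; chance = 1 − (0.513 + 0.351 + 0.111) = 0.025.

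| p | k | q | Expected per row | Chance of 3 or more in a given row |
|---|---|---|---|---|
| 15% | 1 | 0.15 | 1.95 | 31% |
| 15% | 3 | 0.05 | 0.65 | 2.5% |
| 15% | 5 | 0.03 | 0.39 | 0.6% |
| 30% | 1 | 0.30 | 3.9 | 80% |
| 30% | 3 | 0.10 | 1.3 | 13% |
| 30% | 5 | 0.06 | 0.78 | 3.9% |

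Pooling all active subjects (n = 40), the same chances for k = 1, 3, 5 are 95%, 32%, 12% at p = 15% and about 100%, 78%, 43% at p = 30%. The loss is milder there, but SAP 5.1 sets four separate display arms, so the rows for 13 subjects are the relevant ones.

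If subjects report several symptoms each, the rows are fuller than shown. The group incidence still cannot be recovered by adding rows, because the same subject would be counted more than once.

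**The case against.** A reader might infer that the incidence of the five groups will never be produced, that AE-driven stopping of infusions cannot be compared between arms, or that a dose-related reaction would go unseen. The documents support none of these.

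- **Displays.** SAP 8.1 defers details to Appendix 5, which is not supplied and could list such tables. The supportable statement is that the supplied text does not plan them. Against this, 8.1 itself names the by-term tables and their basis, and a display title would still need a definition of each group.
- **Stopping of infusions.** The overview in 8.1 includes action taken for AEs, listed separately from treatment advised. It plausibly counts infusions held or discontinued. What is left is that the categories are not stated.
- **What stays visible.** Each subject counts once for any AE, any serious AE and by relation to treatment, whatever term was used. An excess of drug-attributed events by dose would show there, and all events are listed for 53 subjects. What is lost is incidence specific to the kind of event.
- **Split rows.** The SAP says reported terms and does not call them verbatim. An investigator could record one diagnosis consistently. Splitting is likely, not certain.
- **Weight of the commitment.** The five groups appear once, in the statistical Endpoints paragraph. The formal endpoint lists in the protocol and SAP 2.1 mention only drug-related AEs and SAEs, and the protocol's Safety Analysis section promises number, type and description. This lowers the weight of the point, but none of it withdraws the statement that safety is assessed by those incidences.

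**Conclusion.** The point holds as a mismatch between the protocol and the supplied SAP text. The protocol assesses safety by the incidence of five AE groups; the SAP tabulates by reported term, names no dictionary, and gives no subject-level count for any of the five. The laboratory and vital-sign sections do not fill the gap.

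In arms of about 13, under the assumed incidences of 15% to 30% and an even split over three to five terms, a row expects about 0.4 to 1.3 subjects, against about 2 to 4 when grouped. Those rates and splits are illustrative. The direction follows from the small arms; the exact size depends on how events were worded.

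Overall AE burden remains comparable between arms, so this is a cheap improvement to the safety analysis and not a flaw that invalidates it.

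**What to change.** In SAP 8.1:

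1. Name a coding dictionary and its version, and tabulate all AEs, serious AEs and AEs leading to withdrawal by system organ class and preferred term. Keep reported terms in the listings.
2. Add one table on the safety analysis set giving, for each arm, n (%) of subjects with an exact 95% confidence interval for each of the five groups. Define each group by a term list or laboratory criterion, set by the sponsor and investigators and fixed before unblinding. State whether the protocol's AST/ALT criterion enters the hepatotoxicity definition, and whether results from unscheduled visits count as cases. This table is the essential part: coding merges synonyms, but different symptoms of one reaction would still sit in different rows.
3. Optionally, state that the existing overview of action taken includes categories for infusion held and infusion discontinued. The withdrawal table does not capture patients who stop infusions and stay in follow-up.

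If Appendix 5 already lists such a table, it is enough to add the group definitions and the dictionary and cross-refer to it. The cost is coding the AEs of 53 subjects, agreeing five definitions and programming one extra table. No clinical rule changes.

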8.2. Clinical Laboratory Analyses

Laboratory evaluations including the analyses of Biochemistry laboratory tests, Hematology laboratory tests and Coagulation tests (PTT/PT/INR). The details of the planned displays are in Appendix 5: List of Data Displays.

All laboratory parameters, including numerical urine analysis parameters will be summarised descriptively. Also, p-value for treatment difference using Analysis of variance (ANOVA) is displayed for lab parameters. Categorical urine analysis results will be summarized using count and percentage based on subjects.

Change from baseline will be summarised descriptively. Also, p-value for treatment difference using one-way Analysis of variance (ANOVA) is displayed for change from baseline.

Individual laboratory evaluations will be listed.

Data recorded at unscheduled assessments will not be included in tables and figures but will be listed.

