A complete physical examination (head, eyes, ears, nose, throat, heart, lungs, abdomen, skin, cervical and axillary lymph nodes, neurological, and musculoskeletal systems) will be performed

Allogeneic HB-adMSCs to provide immune support against COVID-19.

at baseline visit. In addition, medical history (including smoking history) will be recorded at baseline.

A limited physical examination to verify continued patient eligibility and to follow up any change in medical history will be performed at the visits indicated in the schedule of assessments. Symptom-driven physical examinations will be performed as clinically indicated at any study visit. All changes not present at baseline or described in the past medical history and identified as clinically noteworthy will be recorded as AEs.

Clinical Laboratory Parameters

The Investigator must review all laboratory reports and document the review. Any laboratory test result or change considered by the Investigator to be clinically significant should be considered an AE and recorded in the AE CRF. Clinically significant abnormal values occurring during the study will be followed until repeat test results return to normal, stabilize, or are no longer clinically significant.

Laboratory tests to be performed during the study:

Complete Blood Count with Differential	IL-6
Chemistry	IL-10
Coagulation study (PTT/PT/INR)	Tumor Necrosis Factor alpha
C Reactive Protein	Rapid Antibody Test for COVID-19

Adverse Events

An AE is any symptom, physical sign or disease that either emerges during the study or, if present at screening, worsens during the study, regardless of the suspected cause of the event. All medical and psychiatric conditions (except those related to the indication under study) present at screening will be documented in the medical history CRF. Changes in these conditions and new symptoms, physical signs, or diseases should be noted on the AE CRF during the rest of the study.

Clinically significant laboratory abnormalities should also be recorded as AEs. Surgical procedures that were planned before the patient enrolled in the study are not considered AEs if the conditions were known before study inclusion; the medical condition should be reported in the patient's medical history.

Serious Adverse Events (SAE)

A serious adverse event (SAE) is any AE that is:

Allogeneic HB-adMSCs to provide immune support against COVID-19.

- fatal
- life-threatening
- requires or prolongs hospital stay

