5.2.1 Change from Baseline

Definition	Reporting Details
Change from Baseline	= Post-Dose Visit Value – Baseline
% Change from Baseline	= 100 x [(Post-Dose Visit Value – Baseline) / Baseline]

NOTES:

- The baseline will be displayed along with Visit name on all summary displays.

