5.3 Examination of Covariates, Other Strata and Subgroups

5.3.1 Covariates and Other Strata

Baseline will be included as a covariate in the efficacy analyses, wherever applicable.

Protocol Number: HBCOVID02
Hope Biosciences
Statistical Analysis Plan

Confidential

Date: 14-Oct-2021
Version: 1.0
Status: Final

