5.5 General Considerations

Unless otherwise stated, all hypotheses will be tested at a 2-sided significance level of 0.05 and 95% confidence interval. All continuous measurements will be summarised descriptively at each visit by treatment using observed data.

Summary of continuous variables will be presented using N, Mean, Standard Error of mean (SE), Standard Deviation (SD), Median and Range (Minimum and Maximum). The categorical variables will be presented using number and percentage based on N.

For measurements over time mean values will be plotted to explore the trajectory over time. LOCF imputed data will be used as the basis for plotting data along with bars as standard error (SE) or Standard Deviation (SD), if not otherwise specified.

Primary endpoints of incidence of COVID-19 symptoms and Hospitalizations due to COVID-19 symptoms will be analysed based on binomial model and p-value will be displayed using two-sample binomial proportion test.

Additionally, time to first incidence of COVID-19 symptoms will analysed using Kaplan-Meir method.

A standard analysis of covariance (ANCOVA) model will be applied for secondary endpoints followed by Tukey's multiple comparison test to test the the significance of the effects of the treatment. The model includes treatment as fixed factor and the corresponding baseline value as a covariate.

Tukey's multiple comparison tests will be tested as two-sided hypotheses at a 5% level of significance. Treatment differences will be confirmed and considered significant if p-value reported is < 0.05 .

Protocol Number: HBCOVID02
Hope Biosciences
Statistical Analysis Plan

Confidential

Date: 14-Oct-2021
Version: 1.0
Status: Final

Presentation of results from a statistical analysis will include the estimated mean treatment effects (Least Square Means (LSMeans)) for absolute values and change from baseline. For all endpoints analysed statistically, estimated mean treatment differences will be presented together with two-sided 95% confidence intervals and p-values obtained using Tukey's method, and results from following paired comparisons will be displayed,

1. HB-adMSCs 200MM vs Placebo
2. HB-adMSCs 100MM vs Placebo
3. HB-adMSCs 50MM vs Placebo

All safety evaluations will be presented using Safety Analysis Set. The efficacy analysis will be presented using Efficacy analysis set.

Individual safety and efficacy parameters will be listed.

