7.2. Secondary Efficacy Analyses

7.2.1. Endpoints / Variables

Change from baseline to the end of study period, Week 26 in,

- Leukocyte differential counts
- C-Reactive Protein
- TNF-alpha
- IL-6
- L-10
- SF-36 questionnaire score

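### SAP 8.2 and 8.3 test laboratory and vital-sign changes without a baseline covariate: valid, but less precise than the ANCOVA the SAP uses elsewhere

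*SAP*

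**What the plan says.** SAP 8.2 says of laboratory tests that a "p-value for treatment difference using one-way Analysis of variance (ANOVA) is displayed for change from baseline", and SAP 8.3 uses the same words for vital signs. Section 8.2 also says that a "p-value for treatment difference using Analysis of variance (ANOVA) is displayed for lab parameters". I read that as the values at each visit; again no covariate is named. SAP 5.2.1 defines change as "Post-Dose Visit Value – Baseline".

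The covariate rule is in SAP 5.3.1: "Baseline will be included as a covariate in the efficacy analyses, wherever applicable". It is confined to efficacy, so sections 8.2 and 8.3 do not inherit it. For secondary endpoints SAP 5.5 specifies ANCOVA: "The model includes treatment as fixed factor and the corresponding baseline value as a covariate". SAP 7.2.4.1 repeats this, with Tukey comparisons.

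SAP 7.2.1 lists "Leukocyte differential counts" among the variables for that ANCOVA, on the efficacy analysis set (participants with all five infusions, SAP 4). Section 8.2 covers haematology on the safety analysis set (anyone dosed) and does not name the differential. The protocol lists "Complete Blood Count with Differential" among the study's laboratory tests (Clinical Laboratory Parameters) and also describes it under Efficacy Assessments.

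**The concern.** Protocol Table 2 schedules blood count, chemistry, coagulation and vital signs at Week 0, so the covariate should be available for nearly everyone. The SAP gives no reason for using a less precise model for safety than for efficacy. Precision matters in a trial this small: the protocol's Determination of Sample Size sets the ceiling of 53 from the number of banked patients, not from power. In a safety comparison the costly mistake is to miss a real shift, and a wider standard error makes that more likely.

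A smaller matter is that leukocyte differential counts may be analysed twice, under 7.2 and as haematology under 8.2, by different models on different analysis sets. The SAP does not say which result serves which purpose.

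**Working it through.** The plan states no power, standard deviation or correlation for any laboratory or vital-sign variable, so there is no figure of its own to reproduce.

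**Inputs from the documents.** Total N = 53 (Protocol, Determination of Sample Size; SAP 2.2); four arms; 3:1 active to placebo (SAP 2.2); two-sided 0.05 (SAP 5.5).

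**Assumptions.** Three equal active arms, so 53/4 = 13.25, taken as 13, 13, 13 and 14. (The synopsis also mentions 25 per group, which would need 4 × 25 = 100 and cannot be met with 53.) Equal variance σ² at baseline and follow-up. Correlation r from 0.3 to 0.9.

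**Variance per participant.**
- Change score: 2σ²(1 - r).
- Visit value: σ².
- ANCOVA: σ²(1 - r²).

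ANCOVA relative to change is (1 - r²)/[2(1 - r)] = (1 + r)/2. ANCOVA relative to the visit value is 1 - r². Estimating the slope multiplies the ANCOVA variance by 1 + 1/(53 - 4 - 2) = 48/47, about 2%.

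| r | ANCOVA / change score | Same, with slope cost | Excess SE of change-score test, before slope cost | ANCOVA / visit value |
|---|---|---|---|---|
| 0.3 | 0.65 | 0.66 | 24% | 0.91 |
| 0.5 | 0.75 | 0.77 | 15% | 0.75 |
| 0.7 | 0.85 | 0.87 | 8.5% | 0.51 |
| 0.9 | 0.95 | 0.97 | 3% | 0.19 |

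The two proportional savings, (1 - r)/2 and r², cross at r = 0.5, where both are 25%. So for any r between 0 and 1, ANCOVA would cut the variance of at least one of the two section 8.2 tests by 25% or more, before the slope cost.

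**Simulation.** Arms of 13, 13, 13 and 14 with no drop-out, 20,000 trials per setting, overall F tests at 0.05. Power is for a 1-SD shift in one arm.

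| r | Type I error: change / ANCOVA | Power: change | Power: ANCOVA | Power: visit value |
|---|---|---|---|---|
| 0.3 | 0.050 / 0.050 | 0.551 | 0.747 | 0.714 |
| 0.5 | 0.047 / 0.048 | 0.710 | 0.835 | 0.717 |
| 0.7 | 0.048 / 0.047 | 0.920 | 0.953 | 0.715 |
| 0.9 | 0.053 / 0.049 | 1.000 | 1.000 | 0.711 |

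**Where the precision goes.** Given an observed baseline difference d between two arms, the change-score estimate is shifted by -(1 - r)d. With 13 per arm the standard error of d is √(2/13) = 0.39 SD, so a one-SE imbalance at r = 0.5 shifts the estimate by 0.5 × 0.39, about 0.20 SD. ANCOVA removes this shift. Averaged over randomisation the shift is zero and the type I error already allows for it.

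**Leukocyte overlap.** On identical participants, the change-score and ANCOVA F tests fell on opposite sides of 0.05 in 5.8%, 4.7%, 3.8% and 2.1% of null trials (r = 0.3, 0.5, 0.7, 0.9), and in 25.6%, 17.1%, 4.9% and 0.0% of trials with the 1-SD shift. The differing analysis sets and the Tukey comparisons were not simulated.

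**The case against.** The strongest reply is that nothing here is wrong in the sense of invalid, and that is correct. A reader might infer that the tests ignore baseline and so produce spurious treatment differences. The documents do not support that: a change score already subtracts baseline (SAP 5.2.1), and under randomisation the test keeps its error rate. Only the ANOVA on visit values makes no use of baseline.

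A reader might also infer that leukocyte counts will get two contradictory p-values. That is not shown. The 7.2 and 8.2 results come from different analysis sets and procedures, so they may differ without contradicting each other. The overlap is itself an inference, because section 8.2 does not name the differential and the list of displays (SAP Appendix 5) is not in the text available.

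Nor do these ANOVAs test a listed secondary endpoint badly. That endpoint is clinically significant change (SAP 2.1), which the investigator judges participant by participant and records as an adverse event (Protocol, Clinical Laboratory Parameters). A comparison of means, adjusted or not, addresses something else.

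Finally, the gain over the change score is small if r is high, no decision rule uses these p-values, and SAP 5.4 calls the testing exploratory. All of this limits the importance of the point. It supplies no reason to prefer the less precise model, and at high r it is the visit-value test that loses most.

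**Conclusion.** The point holds as a minor improvement. The post-baseline p-values in SAP 8.2 and 8.3 come from valid tests that are less precise than the ANCOVA the SAP already specifies. The cost in variance is 5% to 35% for change scores and 9% to 81% for visit values over r = 0.3 to 0.9. These figures rest on equal variances at the two visits and on values of r that the documents do not supply. The power figures also assume about 13 per arm with no drop-out; the synopsis allows 15%, which would leave about 45 (53 × 0.85 = 45.05) and lower them.

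This concerns the precision of safety displays and gives no ground for calling the trial's conclusion biased. For the leukocyte differential, what remains is a missing sentence on which result carries the efficacy inference.

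**What to change.** In SAP 8.2 and 8.3, replace the post-baseline ANOVA p-values with ANCOVA on the safety analysis set, with treatment group and the baseline value as terms. Show the adjusted difference of each dose group from placebo with its 95% confidence interval. With baseline in the model, the analysis of the visit value and the analysis of change give the same treatment difference, so one result replaces the two now planned in 8.2.

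If the leukocyte differential is displayed under 8.2 as haematology, keep that safety-set display, use the same adjusted model, and add a sentence that the 7.2 result is the efficacy inference for that endpoint. It would be a mistake to make 7.2 the only comparison: its analysis set excludes anyone with fewer than five infusions, including those who stopped for safety reasons.

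The cost is a few lines of SAP text and revised table shells. No new data or participants are needed, and the model is already specified in SAP 5.5 and 7.2.4.1. Participants without a baseline drop out of the adjusted analysis. They already have no change score (SAP 5.2), so only the visit-value comparison could lose anyone, and their values remain in the listings.
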